#### **4.1.2. Inclusion Criteria**

Deviations from the inclusion criteria are not allowed because they can potentially jeopardize the scientific integrity of the study, regulatory acceptability or subject safety. Therefore, adherence to the criteria as specified in the protocol is essential.

Subjects eligible for enrolment in the study must meet all of the following criteria:

1. Signed written informed consent.
2. Histologically or cytologically confirmed HER2-positive advanced or metastatic breast cancer which has progressed following prior therapy, which must have included anthracyclines and taxanes and therapy with trastuzumab in the metastatic setting.
3. Females age  $\geq 18$  years old.
4. Eastern Cooperative Oncology Group (ECOG) performance status 0-2 ([Appendix 4](#)).
5. Life expectancy of at least 12 weeks.
6. Able to swallow and retain oral medications.

7. Incapable of becoming pregnant, or not pregnant and using an adequate form of contraception, i.e. a female who is of:
  - a. non-childbearing potential (physiologically incapable of becoming pregnant), including any female who has had hysterectomy, bilateral oophorectomy, bilateral tubular ligation or is post-menopausal (total cessation of menses for at least 1 year);
  - b. childbearing potential must have a negative serum pregnancy test within 7 days prior to treatment with octreotide if randomised to receive octreotide or the first dose of lapatinib with capecitabine if randomised to receive no octreotide, preferably as close to the first dose as possible, and must agree to use adequate contraception (intrauterine device, birth control pills unless clinically contraindicated, or barrier device) during the study and continuing for at least 4 weeks after the final dose of treatment with lapatinib and capecitabine. Acceptable contraceptive methods are described in Section 7.5.1.
8. Subjects must complete all screening assessments as outlined in the protocol.
9. Subjects must complete the FACIT-D and diarrhoea diary before receiving the first dose of octreotide if randomised to receive octreotide. All subjects must complete the FACIT-D and diarrhoea diary before receiving the first dose of lapatinib with capecitabine.

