**Table 19 Evaluation of overall response for subjects with non-measurable only disease at screening**

Non-Target Lesions	New Lesions	Overall Response
CR	No	CR
Non CR/Non PD	No	Non CR/Non PD
NE	No	NE
Unequivocal PD	Yes or No	PD
Any	Yes	PD
CR=complete response, PD=progressive disease, and NE=Not Evaluable		

Subjects with a global deterioration of health status requiring discontinuation of treatment without objective evidence of disease progression at that time should be classified as having "symptomatic deterioration". Objective response status is determined by evaluations of disease burden. Every effort should be made to document the objective progression.

In some circumstances, it may be difficult to distinguish residual disease from normal tissue. When the evaluation of CR depends on this determination, it is recommended that the residual lesion be investigated (fine needle aspirate/biopsy) to confirm the CR.

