## **Overall Response Rate**

Overall response rate (ORR) is defined as the percentage of subjects achieving either a confirmed complete (CR) or partial (PR) tumour response. The ORR will be calculated from the investigator's assessment of response. Subjects who do not have measurable disease or have an unknown or a missing response will be treated as non-responders when calculating the percentages and will contribute to the response rate-based analyses for the evaluation of CR, PR, stable disease (SD) and progressive disease. The ORR in each treatment arm and corresponding 95% confidence interval will be presented.

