## **Clinical Benefit Response**

Clinical benefit response (CBR) is defined as the percentage of subjects with a CR, PR or SD for at least 24 weeks. The CBR will be calculated using the same methods as described for the ORR, i.e. from the investigators assessment of response, subjects who do not have measurable disease, missing or unknown will be treated as non-responders. The CBR in each treatment arm and corresponding 95% confidence interval will be presented.

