2.6.1.5 Response

Response is a secondary aim of this study, as the sample size is relatively small and the study is not powered to detect a statistically significant difference in the response rate or the efficacy of lapatinib and capecitabine for octreotide vs. no octreotide subjects. However, overall response rate and clinical benefit response rate will be presented for interest. RECIST data to assess tumour size and new tumours will be collected as per clinical practice throughout the study. Data will be collected at baseline (screening) and end of 24 weeks of lapatinib and capecitabine treatment. Therefore overall response rate will be presented as response following 24 weeks of treatment, as subjects will not be followed up to progression or death. Therefore, the results of this analysis should be treated with caution and are for interest and exploratory purposes.

Overall response rate (ORR)

Overall response rate (ORR) is defined as the percentage of subjects achieving either a confirmed complete (CR) or partial (PR) tumour response at the end of the study (End of Study/Withdrawal visit). This will be based on the investigator's assessment of overall response.

Subjects with a not evaluable (NE) or missing response will be treated as non-responders; i.e. they will be included in the denominator when calculating the percentage.

The 95% CI for response rates in each group will be provided for the difference in response rates, as for the primary endpoint.

Clinical benefit response

Clinical benefit response (CBR) is defined as the percentage of subjects with a CR, PR or stable disease (SD) for at least 24 weeks. The CBR will be calculated using the investigator's assessment of response. Subjects who do not have measurable disease, or who have a missing or NE response will be treated as non-responders. The CBR in each treatment group and corresponding 95% confidence interval will be presented.

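### SAP 2.6.1.5 fails non-measurable disease for clinical benefit but not for overall response, so a confirmed CR can count in ORR and not in CBR

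*SAP*

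**What the plan says.** Eligibility rests on "Histologically or cytologically confirmed HER2-positive advanced or metastatic breast cancer which has progressed following prior therapy" (Protocol 4.1.2). Neither 4.1.2 nor 4.1.3 asks for measurable disease.

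Protocol 7.1.11 has a separate table, "Evaluation of overall response for subjects with non-measurable only disease at screening" (Table 19). Its possible overall responses are CR, Non CR/Non PD, NE and PD. Protocol 7.2 says disease status is categorised from Tables 18 and 19.

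Protocol 9.3.5.1.2 treats the two endpoints alike. For ORR: "Subjects who do not have measurable disease or have an unknown or a missing response will be treated as non-responders". For CBR: "subjects who do not have measurable disease, missing or unknown will be treated as non-responders".

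SAP 2.6.1.5 does not. ORR is the "percentage of subjects achieving either a confirmed complete (CR) or partial (PR) tumour response at the end of the study", taken from the investigator's overall response, and the only failures it names are these: "Subjects with a not evaluable (NE) or missing response will be treated as non-responders". For CBR, defined as a CR, a PR, or stable disease lasting 24 weeks or more, it says: "Subjects who do not have measurable disease, or who have a missing or NE response will be treated as non-responders".

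SAP section 4, which lists changes from the protocol, mentions the shorter endpoint list and the listing-only handling of the diary. It does not mention the ORR rule.

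**The concern.** CBR adds durable stable disease to the responses that make up ORR, so every ORR responder should also be a CBR responder. Under the SAP text that nesting can fail: a patient with non-measurable disease and a confirmed CR succeeds on one endpoint and fails on the other.

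A programmer following the section literally would produce two endpoints that contradict each other for that patient. The change from the protocol that creates the mismatch is undeclared, although Protocol 9.3.5 asks for deviations from its planned analysis to be documented. At stake is the coherence of the response tables in a small trial in which octreotide delays the start of cancer treatment by 7 days.

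**Working it through.** The documents give no response rate and no non-measurable share for this trial, so there is no planned figure to reproduce. The check is mainly a comparison of rules.

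**Step 1. Each Table 19 outcome under the four written rules** (patient without measurable disease):

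| Overall response | Protocol ORR | Protocol CBR | SAP ORR | SAP CBR |
|---|---|---|---|---|
| Confirmed CR | fails | fails | **responds** | fails |
| Non CR/Non PD through 24 weeks | fails | fails | fails (not CR or PR) | fails |
| NE or missing | fails | fails | fails | fails |
| PD | fails | fails | fails | fails |

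Only one cell differs. The protocol columns agree with each other; the SAP columns disagree on the confirmed CR.

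**Step 2. Direction of the CBR rule.** Let q be the share with non-measurable disease, b the CBR in measurable disease, and n the benefit rate in non-measurable disease when scored from Table 19.

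- CBR under the SAP rule = (1 − q) × b
- CBR scored from Table 19 = (1 − q) × b + q × n
- Shortfall = q × n, which is never negative

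If only Table 19 CRs count as benefit, n is just the CR rate. Non CR/Non PD adds to n only if the SAP separately declares it to be clinical benefit.

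**Step 3. Illustration only.** Assume q of 10% to 30%, Non CR/Non PD counted as benefit, and n equal to the lapatinib plus capecitabine CBR in Protocol Table 1 (29% independent, 37% investigator).

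- 0.10 × 0.29 to 0.30 × 0.29 = 2.9 to 8.7 points
- 0.10 × 0.37 to 0.30 × 0.37 = 3.7 to 11.1 points
- Wider assumptions (q 5% to 30%, n 20% to 50%): 0.05 × 0.20 to 0.30 × 0.50 = 1.0 to 15.0 points
- Shares of 10% in one arm and 30% in the other: 0.20 × 0.29 to 0.20 × 0.37 = 5.8 to 7.4 points between arms

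The SAP introduction reports 62 enrolled at the interim, about 31 per arm at 1:1. One patient is 1/31 = 3.2 points, so the last gap is about 2 patients (0.058 × 31 = 1.8; 0.074 × 31 = 2.3).

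**Step 4. Could the arm totals reverse?** ORR exceeds CBR only if the CR rate in non-measurable disease is above (1 − q) × (b − r)/q, where r is the ORR in measurable disease. With the investigator figures from Protocol Table 1 (r = 31.8%, b = 37%), that threshold is 98.8% at q = 5%, 46.8% at 10%, 20.8% at 20% and 12.1% at 30%.

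**The case against.** The CBR rule was not introduced by the SAP. The protocol scores non-measurable disease as non-response for both endpoints and in both arms, which is a coherent and conservative convention. SAP 2.6.1.5 calls the response results exploratory, plans no test of CBR, and the report is abbreviated after a futility stop. All of this stands, and it limits the severity.

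Four stronger readings are tempting, and the documents do not support them.

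- A reader might infer that CBR is biased low by 3 to 11 points. The share is assumed. The 29% and 37% are whole-population rates from another study, and the protocol does not say how that study scored non-measurable disease. Most of the amount also depends on counting Non CR/Non PD as benefit, which the written CBR definition does not do.
- A reader might infer a false difference between arms of 6 to 7 points. That needs 10% against 30%, a gap of about 6 patients. At a common 20% share the SD of the difference in counts is √(2 × 31 × 0.2 × 0.8) = 3.15, and 5.5/3.15 = 1.75 gives a two-sided probability of about 8%. The 95% half-width for a CBR difference is itself 1.96 × √(2 × 0.29 × 0.71/31) = 23 points, or 24 at 37%.
- A reader might infer that ORR will exceed CBR in an arm. Step 4 shows this is unlikely unless q is large.
- A reader might infer that ORR and CBR are the only evidence on cancer treatment. The SAP also summarises reasons for stopping treatment (2.3.1), compliance (2.6.1.4), exposure and dose changes (2.7.1.2) and deaths by cause (2.7.4).

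A further objection is that widening the responder definition now, after the futility result and in an open-label trial, is unattractive. That is fair, and it is why restoring the protocol's clause is an acceptable alternative. None of these arguments explains why the SAP changed one endpoint and not the other without saying so.

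**Conclusion.** The inconsistency is real as written and minor. A confirmed CR in a patient without measurable disease would count in ORR and not in CBR, and the SAP departs from the protocol's ORR rule without declaring it. This takes the 24-week condition in the CBR definition to apply to stable disease, and it bites only if such a CR occurs.

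Relative to scoring from Table 19, the CBR rule can only lower CBR. It does so by the same rule in each arm, so it favours neither by design. Its size is unknown because the non-measurable share is not given; the point ranges above are illustrations under assumed shares, not estimates for this trial.

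**What to change.** In SAP 2.6.1.5, apply one rule to ORR and CBR.

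- Preferred: score both from Protocol Tables 18 and 19, so that a Table 19 CR counts in both. Remove the measurable-disease condition from the CBR non-responder rule, and state explicitly whether Non CR/Non PD for at least 24 weeks is clinical benefit. Removing the condition alone would leave that category undefined for CBR. Settle it without reference to results by arm.
- Alternative: put the protocol's measurable-disease clause back into the SAP ORR rule. This uses existing text and also removes the contradiction.

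Either way, keep all ITT subjects in the main denominator, report the number with non-measurable disease per arm, and add a line restricted to subjects with measurable disease at baseline. Record the choice in SAP section 4.

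The cost is a few lines of SAP wording and a little extra table output. Target and non-target lesions are already recorded at baseline (Protocol 7.1.2), so no new data are needed.

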2.6.2 Patient-reported outcomes

These analyses will be based on data reported by the patient in the DMD and FACIT-D (see [Section 2.6.2.1](#) and [Section 2.8.1](#)). Analyses of secondary patient-reported diarrhoea-related endpoints will be presented for the ITT populations for patients completing the baseline and at least one post-baseline assessments. Missing data will be treated as missing, i.e. there will be no imputation of missing data.

2.6.2.1 DMD

A by-patient listing of all DMD data will be presented.

2.7 Safety analyses

Unless otherwise specified, all the safety analyses will be based on the Safety population and summaries will include all events or assessments collected during the study. All the summaries will be presented by treatment group.

2.7.1 Extent of Exposure

Extent of exposure to octrotide, lapatinib and capecitabine will be summarized separately.

2.7.1.1 Octreotide

The number and percentage of subjects who received a given number of infusions of octreotide (an infusion is defined as one dose of 20mg, patients should have two 20 mg infusions per dose) (0, 1, 2, 3, 4, >4 20mg infusions) will be reported. The duration of exposure to study treatment in days, calculated as (last dose of octreotide – first dose of octreotide +1), will also be summarised.

Dose intensity (total dose delivered i.e. two 20 mg infusions per dose) will be summarized using mean, median, standard deviation, minimum, and maximum.

The number of subjects with dose reductions, dose escalation, dose delays or missed doses will be summarized using frequency and percentages.

2.7.1.2 Lapatinib and capecitabine

The duration of exposure to lapatinib and capecitabine in weeks will be derived as described in [Section 2.1.3.5](#) and will be summarised. Descriptive statistics including mean, median, standard deviation, minimum, and maximum will be calculated for weeks on study treatment. Moreover, time on study treatment will be categorized in different time periods: ≤ 3 weeks, $>3-6$ weeks, $>6-9$ weeks, $>9-12$ weeks, $>12-24$ weeks, >24 weeks.

The subject's average daily dose, defined as the cumulative dose divided by the duration of exposure for each subject, will be summarized. In addition, summary of the population level daily dose will also be provided. In this analysis, a dose on each day for each subject will be treated as an observation and the summary will be based on the dose on each individual day for all subjects.

Dose reductions will be summarised by number of reductions and reasons for reductions. Dose escalations will be summarised by number of escalations and reasons for escalation. Dose interruptions will be summarised by number of interruptions and reasons for the interruptions. The mean, standard deviation, median, minimum, and maximum will be computed for the duration of interruptions. The summaries of dose modifications will be provided only if there is sufficient data.

All the dose reductions, dose escalations, missed doses and dose delays will be listed separately for octreotide, lapatinib and capecitabine.

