Therapeutically relevant circulating concentrations of octreotide should be achieved 7-14 days after the first dose of octreotide LAR, and should be maintained for at least four weeks following the second dose of octreotide LAR. The dose of octreotide LAR employed in LAP117314, 40mg, is higher than the standard starting dose of octreotide LAR, 20mg, in order to achieve clinically relevant circulating concentrations of octreotide more rapidly, reducing the delay required before the start of treatment with lapatinib and capecitabine. The primary analysis of efficacy will be based on data from the first three cycles of treatment with lapatinib and capecitabine (ie up to 9 weeks), when circulating concentrations of octreotide are predicted to be within the clinically relevant range. Supplementary analyses of efficacy will be based on the subsequent period of the study (ie nominally from week 12 to week 24) and for the total duration of the study (ie from the start of treatment with lapatinib and capecitabine to week 24).

It is unknown how accurately AE reporting within the context of a clinical study reflects the actual incidence of AEs. It is possible that the incidence of diarrhoea associated with cancer treatment is under-reported when recorded by investigators at each study visit, particularly if episodes of diarrhoea are mild or isolated. The completion of diaries by subjects to record episodes of diarrhoea may more accurately reflect the true incidence of these events.

In this study, the frequency and severity of diarrhoea will be recorded by the completion of AE forms in the eCRF by the investigator in a manner consistent with the method of AE recording used in previous studies. Episodes of diarrhoea and the effects of diarrhoea will also be evaluated indirectly by assessing the use of anti-diarrhoeal medication, treatment compliance, unscheduled visits to healthcare professionals, and the use of rehydration therapy as recorded in the eCRF.

In addition, subjects will complete the Diarrhoea Management Diary (DMD), which will collect information on the frequency and form of bowel movements, and information on the actions taken as a result of diarrhoea. Subjects will also complete the Functional Assessment of Chronic Illness Therapy-Diarrhoea (FACIT-D), which includes a sub-scale related to diarrhoea, to determine the effects of octreotide on quality of life during treatment with lapatinib and capecitabine.

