#### 1.3.1. Risk Assessment

The analysis of risk associated with octreotide treatment in LAP117314 is based primarily on potential risks identified in the [Octreotide SPC](#). These risks are considered relative to the subject population and study treatments and procedures in LAP117314.

Octreotide LAR is approved for use in patients in whom initial treatment with octreotide in the formulation for s.c. injection has been shown to be effective and well tolerated. Prior treatment with octreotide is not required for subjects to be enrolled in LAP117314, and the tolerance to treatment with octreotide is unlikely to be known for most subjects

prior to enrollment in the study. Subjects randomised to receive octreotide must receive one 0.1mg dose of octreotide by s.c. injection to assess tolerability at least one hour before the first dose of the LAR formulation is administered. Following s.c. administration of octreotide, peak circulating concentrations are achieved within 30 minutes, and the elimination half life of octreotide is approximately 100 minutes [Octreotide SPC]. This single s.c. dose of octreotide should identify subjects who have a hypersensitivity reaction to octreotide or its' excipients (the only contraindication for the use of octreotide).

Treatment with octreotide in both the s.c. and LAR formulations is generally well tolerated [McKeage, 2003]. Adverse events related to the mechanism of action of octreotide have been reported, including hyperglycaemia, hypoglycaemia, impaired glucose tolerance, hypothyroidism, thyroid dysfunction and cholelithiasis. These mechanism-related AEs tend to be associated with chronic treatment with octreotide [Octreotide SPC], and are therefore unlikely to be relevant within the context of LAP117314. In this study, octreotide will be administered as only one dose of the s.c. formulation and two doses of the LAR formulation over a period of 28 days, and the total duration of exposure to clinically relevant concentrations of octreotide is expected to be no more than 12 weeks.

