#### **4.3.3. Subject Completion**

A subject will be considered to have completed the study if the subject completes 24 weeks of treatment with lapatinib and capecitabine, or if cancer progresses or the subject dies during treatment, whichever is sooner. The cause of death must be recorded in the eCRF. A subject will be considered to have withdrawn from the study prematurely if

treatment is permanently stopped due to toxicity, or the subject has withdrawn consent, or the subject is no longer being followed at the investigator's discretion.

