### 5.2.1. Capecitabine Dosage and Administration

The capecitabine dose schedule is an intermittent regimen consisting of 2 weeks of treatment followed by a 1 week drug-free period. The starting dose of capecitabine in combination with lapatinib will be 2000mg/m^2/day. This is to be divided to 1000 mg/m^2 per dose and given twice daily orally, 12 hours apart, for 14 days, every 21 days. Study staff will carefully instruct subjects on how to take capecitabine and the correct dose to be taken.

The capecitabine morning dose must be taken with food or within 30 minutes after a breakfast meal with approximately 200ml of water. The capecitabine evening dose should be taken approximately 12 hours after the morning dose and should be taken with food, or within 30 minutes after food, with approximately 200ml of water.

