2.1.3.5 Duration/Elapsed Time/Time unit

Durations (e.g., the duration of an adverse event, duration of exposure, duration of episodes of diarrhoea) are calculated as the stop date minus the start date +1.

For elapsed time (e.g., the time since initial diagnosis):

- If the reference start date is on or after the event date, then the elapsed time is the reference start date minus the event date + 1.
- If the reference start date is before the event date then the elapsed time is the reference start date minus the event date.

A year length is defined as 365.25 days. A month length is 30.4375 days (365.25/12). If duration is reported in months, duration in days will be divided by 30.4375. If duration is reported in years, duration in days will be divided by 365.25.

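### Capecitabine average daily dose is divided by calendar days, so with perfect adherence it falls from 2000 to 1391 mg/m²/day as cycles accrue (minor; descriptive tables only)

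*SAP*

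**What the plan says.** **Capecitabine.** SAP 2.7.1 summarises exposure separately for each drug. For lapatinib and capecitabine, section 2.7.1.2 takes duration from section 2.1.3.5, where durations (exposure is one of the named examples) "are calculated as the stop date minus the start date +1". The subject's "average daily dose, defined as the cumulative dose divided by the duration of exposure for each subject, will be summarized". The same section adds a population-level daily dose in which each subject's dose on each day is one observation.

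Protocol 5.2.1 describes the regimen: "The capecitabine dose schedule is an intermittent regimen consisting of 2 weeks of treatment followed by a 1 week drug-free period". The dose is 1000 mg/m² "given twice daily orally, 12 hours apart, for 14 days, every 21 days".

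The SAP does not say how rest days enter either summary, or which date is the capecitabine stop date. Its nearest conventions point to the last dose. Section 2.1.3.3 defines last administration as the last date with a nonzero dose, and section 2.4.1 counts the lapatinib duration from first to last dose date. Section 5.1.3.2 replaces a missing end date, for a subject still on drug, with the End of Study/Withdrawal visit date.

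**Octreotide.** SAP 2.7.1.1 gives exposure in days, "calculated as (last dose of octreotide – first dose of octreotide +1". Protocol 1.2 expects that effective concentrations "should be maintained for at least four weeks following the second dose of octreotide LAR", and Protocol 1.3.1 states that "the total duration of exposure to clinically relevant concentrations of octreotide is expected to be no more than 12 weeks".

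**The concern.** Dividing by calendar days is harmless for a drug taken every day. For a drug with a planned rest week in each cycle, the divisor grows by 21 days per added cycle while the dose grows by 14 days' worth. Only the first cycle is counted without a rest week, so the average must fall as cycles accumulate.

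A reader takes average daily dose as a sign of how fully the planned dose was delivered. SAP 2.4.1 invites this by saying that the exposure and dose-modification summaries will further characterise compliance. Under the present formula, a low value may mean reduced or missed doses, or simply long treatment. Protocol 9.3.5.2.1 expects effective prophylaxis to lengthen exposure to lapatinib and capecitabine, so the two explanations would be mixed in the table where a reader would look.

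For octreotide, a span that ends on the day of the last depot dose is the time between doses. It is not the time under the drug's effect as the protocol describes it.

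**Working it through.** The plan states no average daily dose, so there is no figure of its own to reproduce.

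**Inputs.** Dose on a dosing day: 2 × 1000 = 2000 mg/m² (Protocol 5.2.1). Schedule: 14 days on, 7 off. Maximum: 24 weeks, or 8 cycles; Protocol 4.3.3 counts as a completer a subject who "completes 24 weeks of treatment with lapatinib and capecitabine". Stop date: taken as the last dosing day.

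**Perfect adherence, k complete cycles.**
- Cumulative dose = 2000 × 14 × k = 28000k mg/m².
- Duration = 21(k − 1) + 14 = 21k − 7 days.
- Average = 28000k / (21k − 7).

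| Cycles | Days | Average, mg/m²/day |
|---|---|---|
| 1 | 14 | 2000 |
| 2 | 35 | 1600 |
| 3 | 56 | 1500 |
| 4 | 77 | 1455 |
| 5 | 98 | 1429 |
| 6 | 119 | 1412 |
| 7 | 140 | 1400 |
| 8 | 161 | 1391 |

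From one cycle to eight the fall is (2000 − 1391)/2000 = 30%, with no missed dose.

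**Other stop dates.**
- Mid-cycle: the lowest value for a perfectly adherent subject comes when the last dose is on the first day of cycle 8 (day 148). It is (7 × 28000 + 2000)/148 = 198000/148 = 1338.
- End date imputed to the end of Week 24 (day 168): 224000/168 = 1333.
- Stop date recorded as the end of each 21-day cycle: 28000k/21k = 1333 for every k, with no drift.

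**Ranking.** One full cycle, one cycle at 75% and then a stop gives (28000 + 21000)/35 = 1400. Eight perfect cycles give 1391. The subject with the reduced dose ranks higher.

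**Population-level daily dose.** Over the same 161 days, a perfect eight-cycle subject has 112 dosing days and 49 rest days. Counting rest days as zero gives a mean of 224000/161 = 1391; leaving them out gives 2000. The SAP does not say which applies.

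**With scheduled dosing days as divisor.** Every perfectly adherent subject averages 28000k/14k = 2000. The stop on day 148 gives 198000/(7 × 14 + 1) = 2000. The subject with one full and one 75% cycle gives 49000/28 = 1750, or 87.5% of the protocol dose.

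**Octreotide.** One LAR dose: 0 + 1 = 1 day. Two doses 28 days apart: 28 + 1 = 29 days, or 27 to 31 with the ±2-day window in the SAP schedule. Four weeks after the second dose is day 28 + 28 = 56, and the protocol's ceiling of 12 weeks is 84 days. Twenty-nine days is 52% of 56 and 35% of 84.

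**The case against.** The best counter-argument is that the 2000-to-1391 series depends on one reading of the stop date. Section 2.1.3.5 does not say last dose, and the layout of the dosing record is not shown. If a record closes at the end of the cycle, the average is a constant 1333. It could also be argued that both drugs share one span, since they are permanently discontinued together and lapatinib continues through the rest week. This stands as a reason to call the text ambiguous. It does not remove the point: section 2.7.1 says the drugs are summarised separately, the SAP's explicit conventions use the last dose, and the imputation in section 5.1.3.2 gives subjects still on drug a different kind of end date from those who stopped.

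The second argument is that little rests on these tables, and it largely stands. Compliance in section 2.4.1 is cumulative actual over cumulative planned dose, so rest days do not distort it provided their planned dose is zero. Weeks on treatment, reductions and interruptions are tabulated alongside, so longer treatment would be visible. No between-arm test of average daily dose is planned.

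Two stronger inferences are tempting but unsupported:
- **Adverse events in the depot period appear to be off drug.** They do not. The octreotide duration classifies no event. Section 2.1.3.10 runs the on-treatment window to 28 days after the last dose of any component, and section 2.7 includes all events collected during the study.
- **The arm comparison is biased by a known amount.** The formula does lower the mean in an arm that stays on capecitabine longer. Its size would need discontinuation patterns that the documents do not give.

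On octreotide, the SAP already tabulates the number of 20 mg administrations and the total dose, which largely describe a two-dose regimen. The duration adds little beyond them, but as labelled it can be misread.

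**Conclusion.** The point holds for capecitabine. As written, and with the last dosing day as stop date, average daily dose is a function of the number of cycles: 2000 down to 1391 mg/m²/day for one to eight perfect cycles, as low as 1338 for a mid-cycle stop and 1333 with the end date imputed to Week 24. It can place a subject with a reduced dose above one who took every tablet. This assumes 14-of-21-day dosing without delays, and the size rests on the stop-date reading; if the dosing record closes each cycle at day 21, the drift disappears.

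The octreotide duration is a labelling matter: 1 or 29 days is correct as time from first to last dose and wrong as time exposed to a depot.

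Severity is minor. These are descriptive summaries in an abbreviated report. The primary analysis, adverse event classification and compliance percentage do not use these quantities.

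**What to change.** In SAP 2.7.1.2, for capecitabine only:
- Divide cumulative actual dose (mg/m²) by the number of scheduled dosing days, Days 1 to 14 of each cycle, from first dose to treatment discontinuation or the end of study treatment. Alternatively, report the cumulative dose as a percentage of the protocol dose over those days.
- State whether cycle days follow the planned 21-day calendar or each cycle's actual start, so that the handling of cycle delays is explicit.
- In the population-level daily dose, exclude scheduled rest days and keep missed dosing days as zero.

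Two simpler alternatives should be avoided. Dividing by 21 × cycles started penalises mid-cycle stops: a subject who stops after one day would average 2000/21 = 95. The last contact date (SAP 2.1.3.9) is not a dosing date and should not end the count.

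In SAP 2.7.1.1, either label the octreotide figure as time from first to last LAR dose, or define it as last LAR date plus 28 days minus first LAR date, giving 28 and 56 days. The second option adds 27 days to every LAR-treated subject on schedule, so relabelling is enough if the dose counts are kept.

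The cost is a few lines of SAP text and two or three derivations. Protocol 5.8 already has treatment start and stop dates, delays and reductions recorded in the eCRF, so no new data are needed.
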